#### **13.4.1.5 Progression-Free Survival**

PFS is measured from the start of moxetumomab pasudotox administration to relapse, PD, or death from any cause. Relapse is considered post-end of treatment when patients no longer meet criteria required for their best response (Section 11.1). PFS will be censored on the last hematologic assessment for subjects without relapse, PD, or death. PFS will be evaluated using the Kaplan-Meier method.

#### **13.4.1.6 Time to Treatment Failure**

TTF will be measured from the start of moxetumomab pasudotox administration until relapse, PD, initiation of alternate cancer therapy, or death due to disease or disease-related complication. ([Else et al, 2009](#)). TTF will be censored as in PFS but will also be censored for death not accompanied by relapse, and will also be evaluated using the Kaplan-Meier method.

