#### **13.4.1.1 CR Rate, Duration of CR (Disease-Free Survival), and Duration of Hematologic Remission**

The CR rate is defined as the proportion of subjects that have achieved CR. The 95% CI of the CR rate will be constructed using the exact probability method (Clopper-Pearson exact interval). Duration of CR (also called disease-free survival) will be measured from the first documentation of CR (by imaging, bone marrow biopsy and blood counts) to the time of relapse as defined in Section 11.1. Duration of HR will be measured from the first documentation of CR (by imaging, bone marrow biopsy and blood counts) to the time of loss of HR. Duration of CR will be censored on the date of the last disease assessment or clinical

response assessment for subjects who have no documented relapse prior to data cutoff, dropout, or the initiation of alternative anticancer therapy. Duration of HR will be censored on the date of the last evaluable hematologic assessment for subjects who have no documented loss of HR prior to data cutoff, dropout, or the initiation of alternative anticancer therapy. The proportion of subjects with a CR and HR at certain time points (eg, 6 month, 1 year, or 2 year) and the median duration of CR and HR may be estimated, if feasible, for the subgroup of subjects with CR using the Kaplan-Meier method. It should be noted that CR duration, which may be shorter than HR duration, is a secondary endpoint and will be summarized separately.

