#### **13.4.1.4 Duration of Objective Response**

Duration of objective response will be measured from the first documentation of objective response to the event of relapse as defined in Section 11.1. Duration of objective response will be censored on the date of last disease assessment for subjects who have no documented relapse prior to data cutoff, dropout, or the initiation of alternative anticancer therapy. Duration of objective response will be summarized descriptively by using minimum and maximum of duration of objective response observed at a certain follow-up period. The proportion of subjects with response at certain time points (eg, 6 month, 1 year, or 2 year) and the median duration of response may be estimated, if feasible, for the subgroup of subjects with objective response using the Kaplan-Meier method.

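### The TTF definition both counts and censors a disease-related death without relapse or PD, and the duration of CR labelled disease-free survival has no death event

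*Protocol*

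**What the plan says.** Protocol Section 13.4.1.6 runs TTF from the start of dosing "until relapse, PD, initiation of alternate cancer therapy, or death due to disease or disease-related complication". The following sentence sets the censoring: "TTF will be censored as in PFS but will also be censored for death not accompanied by relapse". TTF is then estimated by Kaplan-Meier.

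Section 13.4.1.5 treats deaths differently: "PFS is measured from the start of moxetumomab pasudotox administration to relapse, PD, or death from any cause", and "PFS will be censored on the last hematologic assessment for subjects without relapse, PD, or death".

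Section 13.4.1.1 states: "Duration of CR (also called disease-free survival) will be measured from the first documentation of CR". The end point is relapse as defined in Section 11.1. For patients with no documented relapse, "Duration of CR will be censored on the date of the last disease assessment or clinical" response assessment. Section 13.4.1.4 measures duration of objective response "from the first documentation of objective response to the event of relapse as defined in Section 11.1", with matching censoring at the last disease assessment. The relapse definitions in Section 11.1 concern loss of response criteria (or, after stable disease, meeting the PD criteria) and do not mention death.

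**The concern.** Two neighbouring sentences give opposite instructions for the same death. With one arm of 77 patients, a few deaths coded one way or the other are visible in the curve, and the choice could be made after the outcomes are known.

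There is also a question of what the curves estimate. When a patient who has died is censored, Kaplan-Meier treats that patient as still able to fail later, at the same rate as those who remain. The curve then exceeds the proportion of patients alive without failure. In TTF this applies to deaths caused by the study drug, which most readers would regard as treatment failures. In duration of CR it applies to deaths in remission, which a reader who sees the words disease-free survival would expect to be events.

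**Working it through.** **The plan's own figure.** The protocol states no number for TTF or for the response durations. Its only power figure concerns durable CR: 77 subjects, 28% against 13%, two-sided 0.05, 90% power. With n = 77, the smallest count whose 95% Clopper-Pearson lower limit exceeds 13% is 17 (lower limit 13.4%). P(X ≥ 17) is 0.0189 at 13% and 0.903 at 28%. The figure reproduces, and nothing in it uses the rules discussed here.

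**TTF, the two sentences side by side.**

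1. Relapse, PD and alternate therapy are already TTF events. The death limb can add an event only for a patient who dies before any of these.
2. Apart from deaths after relapse, which are already events, the censoring clause covers every death. It therefore takes in the deaths that the death limb was meant to add.
3. Section 11.1 allows PD only during therapy and calls later worsening relapse. A death during treatment cannot, in the protocol's own terms, be accompanied by relapse.
4. The case is realistic. Section 2.2 says that patients with advanced disease are at risk of dying of bleeding or infection through cytopenias. Neutrophils below 1.0 × 10⁹/L alone can qualify a patient under Section 3.1.1, so a patient can die of infection with counts that were low from the start and never fell by the 25% that PD requires.
5. A death from toxicity is not in the event list and meets the censoring clause.

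| Death before relapse, PD or alternate therapy | TTF event list | TTF censoring clause | PFS |
|---|---|---|---|
| Disease or disease-related complication | event | censored | event |
| Treatment-related | not listed | censored | event |

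**Durations.** For duration of CR and of objective response, relapse is the only event and patients without documented relapse are censored at their last assessment. A responder who dies without relapse therefore falls among the censored. This is an inference; no sentence names death as a reason for censoring.

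**Size in TTF (death counts assumed).** Let k of 77 patients die early, before any other event, and let S(t) be the later Kaplan-Meier value with those deaths censored. Counting them gives (1 − k/77) × S(t), so the difference is (k/77) × S(t).

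| k | Ceiling, S(t) = 100% | S(t) = 70% |
|---|---|---|
| 1 | 1.3 points | 0.9 points |
| 2 | 2.6 | 1.8 |
| 4 | 5.2 | 3.6 |
| 6 | 7.8 | 5.5 |

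**The same effect as a rate (assumed).** Take exponential times, independent deaths, a 12-month failure risk of 30% and a 12-month risk d of death without prior failure. With deaths censored, the curve is 70.0% at 12 months (median 23.3 months). With deaths counted it is 0.70 × (1 − d): 68.6%, 66.5% and 63.0% for d = 2%, 5% and 10% (medians 22.1, 20.4 and 18.0 months). The gap is 1.4, 3.5 and 7.0 points.

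**Size in duration of CR (number of CRs assumed).** One early death among n complete responders moves the curve by at most 1/n: 4.5 points for n = 22 and 3.2 points for n = 31. The 22 is 28% of 77 (21.6) rounded up, which is the durable CR assumption and not a CR rate; the 31 is only an assumed upper value.

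**The case against.** The best defence of TTF is that the second sentence was meant to complement the first: disease-related deaths count and all other deaths are censored. That would be coherent, but the text does not say it, because its test is relapse and not cause of death. Toxic deaths would still be censored. The amendment log suggests how the clause arose: the same words appear under Amendment 2 for relapse-free survival, and Amendment 4 records that section being retitled TTF. This explains the clash; the fault is in the current text.

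The overlap is also narrower than all disease-related deaths. Under Section 11.1, a fall of at least 25% in hemoglobin, platelets or neutrophils to below the stated limits is PD unless judged an effect of treatment, so many such patients would already have failed. What remains is deaths with stable cytopenias, or after a fall attributed to treatment.

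Limiting TTF deaths by cause can be a deliberate choice, made with reference to a published source, and so can a relapse-only response duration. Section 13.1 leaves analysis detail to the statistical analysis plan. This stands against any claim that the choice itself is an error. It does not settle two conflicting sentences, and it does not make a relapse-only duration a survival endpoint.

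A reader might infer that the protocol keeps toxic deaths out of all its time-to-event results. It does not: PFS counts death from any cause from the same start date, fatal toxicity is captured in AE and SAE reporting, and the DMC reviews treatment-related mortality. Nor does the protocol expressly censor deaths in remission.

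**Conclusion.** The TTF definition is wrong as written. A disease-related death without documented relapse or PD is both an event and censored, and a treatment-related death is censored, so the curve depends on an unstated coding choice and leans favourable. The disease-free survival label on duration of CR is misleading, on the inference that a death in remission is censored. Duration of objective response has the same structure without the label.

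The size rests on assumed deaths. The shift is about S(t)/77 per early death, with 1.3 points as the ceiling. Two to six deaths give at most 2.6 to 7.8 points, or about 1.8 to 5.5 points where S(t) is 70%. It would be wrong to read 1.3 points as a constant cost per death, since it shrinks as other patients fail.

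Only secondary, descriptive estimates from a single arm are affected. The primary endpoint, the 77 subjects and the 90% power do not change.

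**What to change.** In Section 13.4.1.6, delete the part of the censoring sentence that follows the reference to PFS and state one rule for deaths. Death from any cause as a TTF event is preferable: it needs no judgement on cause of death, and TTF still differs from PFS because starting alternate therapy is an event. At minimum, restrict the censoring clause to deaths not due to disease or a disease-related complication, and analyse those deaths as competing events by cumulative incidence.

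In Section 13.4.1.1, either count death from any cause as an event in duration of CR, or drop the disease-free survival label and report the cumulative incidence of relapse with death as a competing event. State the same choice for duration of objective response in Section 13.4.1.4.

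The cost is a wording change and minor programming. The downside for the sponsor is that TTF and disease-free survival become slightly less favourable if any such deaths occur. The minimum version of the TTF fix also needs a classification of cause of death.

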#### **13.4.2 Safety Assessment**

Safety endpoints include assessment of AEs, SAEs, changes in clinical laboratory evaluations and vital signs. The occurrence of AEs, abnormal laboratory values, and SAEs reported from the first administration of moxetumomab pasudotox through 30 days after last dose of moxetumomab pasudotox will be summarized for all subjects who received any moxetumomab pasudotox. AEs and SAEs will be graded according to the NCI CTCAE V4.0 and described by system organ class and by Medical Dictionary for Regulatory Activities (MedDRA) preferred term, severity, and relationship to moxetumomab pasudotox. Frequency rates will be calculated for each system organ class and MedDRA preferred term.

#### **13.4.3 Pharmacokinetic Assessment**

Individual moxetumomab pasudotox serum concentrations will be tabulated by treatment cycles along with descriptive statistics. Noncompartmental PK data analysis will be performed for Cycle 1 and 2 concentration data using scheduled or actual PK sample collection times.

If data allows, descriptive statistics of noncompartmental PK parameters will be provided.

[REDACTED]

#### **13.4.4 Immunogenic Potential of Moxetumomab Pasudotox**

Immunogenicity results will be listed for each subject. The number and percentage of subjects who develop detectable ADA and NAb will be summarized. Titers and specificity will be reported for NAb-positive subjects. The impact of ADA on PK, safety and efficacy will be evaluated if data allow. Summaries of ADAs and NABs will be provided at the completion of the study and will not be performed on a real-time basis.

### 13.5 Sample Size and Power Calculations

The sample size estimation in this study is based on the assumption that the historical durable CR rate in this population is  $\leq 13\%$  (null hypothesis). [REDACTED], a total of 77 subjects will provide 90% power to detect a difference between 28% and 13% durable CR rates at a 2-sided significance level of 0.05. [REDACTED]

### 13.6 Early stopping Rule Due to Lack of Efficacy

[REDACTED]

### 13.7 Data Monitoring Committee

An external DMC composed of individuals with no involvement in the study will be employed. The committee will review safety data, including AEs, SAEs, treatment-related mortality, and laboratory data. The planned DMC analysis will occur after the first 15 subjects are treated and followed for at least one treatment cycle and every 6 months thereafter until the end of the study. [REDACTED]

[REDACTED] The committee will report its findings to an internal MedImmune safety review committee. In addition, the DMC may be asked by the medical monitor or a MedImmune safety review committee to independently review data on an ad hoc basis. At each review, the DMC will make a recommendation to continue the study with or without modification, or to halt enrollment for safety concerns. This recommendation will be relayed to a MedImmune safety review committee and appropriate action will be taken. Where applicable, regulatory authorities and IRBs/IECs will be notified of any actions taken with the study.

## 14 HUMAN SUBJECTS PROTECTIONS

### 14.1 Ethical Conduct of the Study

The study will be performed in accordance with ethical principles that have their origin in the Declaration of Helsinki and are consistent with ICH/Good Clinical Practice, and applicable regulatory requirements.

### 14.2 Rationale for Subject Selection

Subjects with histologically confirmed HCL will be eligible for participation in this study. Individuals of any race or ethnic group will be eligible for this study. Eligibility assessment will be based solely on the patient's medical status.

### 14.3 Evaluation of Benefits and Risks/Discomforts

#### 14.3.1 Benefits

The potential benefits to patients on this study, based on the results of a completed Phase 1 study in subjects with multiply relapsed HCL, include a high ORR and CR rate that is durable (Section 2.2). This may lead to improved disease-free survival and overall survival compared to available salvage therapies.

#### 14.3.2 Risks

The primary risks of participation in this study include the possible occurrence of any of a range of side effects from moxetumomab pasudotox which are described in Section 2.2 and in the consent document. Frequent monitoring for adverse effects and exclusion of subjects at risk for these adverse effects will help to minimize the risks associated with administration.

##### 14.3.2.1 Important Potential Risks

[REDACTED]

### **Potential Risks Common to Any Immunoglobulin**

Potentially severe or fatal infusion-related reactions and acute IgE-mediated allergic reactions may occur following the administration of any Ig.

Administration of polyclonal Ig preparations and mAbs has been associated with infusion-related reactions that occur during or shortly after dosing such as fever, chills, myalgia, nausea, vomiting, pruritus, rash, headache, flushing, sweating, tachycardia, dyspnea, bronchospasm, hypotension, dizziness or lightheadedness, and hemodynamic instability. These reactions are more common with higher doses, higher rates of infusion, and in subjects with a history of allergies.

IgE-mediated allergic reactions may include hypotension, dyspnea, cyanosis, respiratory failure, urticaria, pruritus, angioedema, hypotonia, and unresponsiveness. Acute severe allergic reactions (anaphylaxis) usually occur soon after exposure, usually within 10 minutes. Subjects may experience paresthesia, hypotension, laryngeal edema, mental status changes, facial or pharyngeal angioedema, airway obstruction, bronchospasm, urticaria and pruritus, serum sickness, arthritis, allergic nephritis, glomerulonephritis, temporal arteritis, and death.

### **Potential Risks Associated with Immune Reactivity**

[REDACTED]

### **Potential Risks Associated with Administration**

Moxetumomab pasudotox is administered IV. Possible risks associated with IV administration of moxetumomab pasudotox are infection, redness, swelling, pain, and induration at the administration site.

#### 14.3.2.2 Identified Risks

[REDACTED]

#### 14.4 Risks/Benefits Analysis

For patients with HCL without effective therapy, median survival is about 4 years.

Moxetumomab pasudotox has shown activity [REDACTED] in patients with multiply relapsed HCL in an early phase clinical trial. [REDACTED]

[REDACTED]

[REDACTED] For these reasons, the risk/benefit ratio of this protocol is favorable; [REDACTED]

[REDACTED]

#### 14.5 Consent Process and Documentation

The investigational nature and objectives of this trial, the procedures and treatments involved and their attendant risks and discomforts, and the potential benefits will be carefully explained to the patient or the patient's advocate. This process will include a general description of the disease process, as well as a description of the patient's expected clinical course. Alternative therapies will be carefully explained, and outlined in the consent document. The patient will be asked to read the consent at his/her convenience and will be encouraged to ask questions. Enrollment on this study will only occur if the patient meets all eligibility criteria, is judged by the Investigator to potentially benefit from the therapy, is able and willing to provide full consent, and has signed the consent document. The PI or an associate investigator on the trial will obtain consent.

#### 14.6 Ethics and Regulatory Review

An IRB/IEC should approve the final study protocol, including the final version of the Informed Consent Form and any other written information and/or materials to be provided to

the subjects. The investigator will ensure the distribution of these documents to the applicable IRB/IEC, and to the study site staff.

The opinion of the IRB/IEC should be given in writing. The investigator should submit the written approval to the sponsor before enrollment of any subject into the study.

The IRB/IEC should approve all advertising used to recruit subjects for the study.

The sponsor should approve any modifications to the Informed Consent Form that are needed to meet local requirements.

If required by local regulations, the protocol should be re-approved by the IRB/IEC annually.

Before enrollment of subjects, the final study protocol, including the final version of the Informed Consent Form, should be approved by or notified to the national regulatory authority, according to local regulations.

The sponsor or sponsor's designee will provide regulatory authorities and PIs with safety updates/reports according to local requirements, including suspected unexpected serious adverse reactions (SUSARs), where relevant.

Each PI is responsible for providing IRB/IECs with reports of SUSARs with the investigational product. The sponsor will provide this information to the PI so that he/she can meet these reporting requirements.

## **14.7 Changes to the Protocol and Informed Consent Form**

If there are any substantial changes to the study protocol, then these changes will be documented in a study protocol amendment and where required in a new version of the study protocol.

The amendment is to be approved by the relevant IRB/IEC and if applicable, also the national regulatory authority, before implementation. Local requirements are to be followed for revised protocols.

MedImmune will distribute any subsequent amendments and new versions of the protocol to each PI. For distribution to IRB/IEC see Section [14.6](#).

If a protocol amendment requires a change to a site's Informed Consent Form, MedImmune and the site's IRB/IEC are to approve the revised Informed Consent Form before the revised form is used.

If local regulations require, any administrative change will be communicated to or approved by each IRB/IEC.

## **14.8 Audits and Inspections**

Authorized representatives of MedImmune, a regulatory authority, or an IRB/IEC may perform audits or inspections at the center, including source data verification. The purpose of an audit or inspection is to systematically and independently examine all study-related activities and documents, to determine whether these activities were conducted, and data were recorded, analyzed, and accurately reported according to the protocol, GCP, guidelines of the ICH, and any applicable regulatory requirements. The investigator will contact MedImmune immediately if contacted by a regulatory agency about an inspection at the site.

## 16 CHANGES TO THE PROTOCOL

### Protocol Amendment 9, 29Mar2017

Text revisions resulting from this amendment are incorporated in the body of Protocol Amendment 9. Major changes to the protocol are summarized below.

1. Section 5.2.1 (Concomitant Medications): Text referring to the time period through which concomitant medications should be collected was changed from 30 days after the last dose of moxetumomab pasudotox to 181 days after the end of treatment of moxetumomab pasudotox. [REDACTED]  
[REDACTED] In addition, text was added to indicate that beyond 181 days after end of treatment until the end of study, only administrations of blood component transfusions and hematopoietic growth factors will be recorded [REDACTED]  
[REDACTED]
2. Table 10-2 (Study Calendar for End of Treatment and Follow-up): Table modified to reflect collection of blood component transfusions and hematopoietic growth factors uses on 12 months, 18 months, and yearly thereafter. Footnote added to indicate that collections on those dates include only blood component transfusions and hematopoietic growth factors uses.

### Protocol Amendment 8, 06Jan2017

Text revisions resulting from this amendment are incorporated in the body of Protocol Amendment 8. Major changes to the protocol are summarized below.

1. Cover page – The medical monitor [REDACTED] was changed to [REDACTED]
2. PRECIS (Background) – [REDACTED]  
[REDACTED]  
[REDACTED]  
[REDACTED]
3. Section 11.1 (Response Criteria – Complete Response with or without Minimal Residual Disease) – The text referring to requirements for CR ± MRD that need to be present was changed from “No evidence of leukemic cells by routine H/E stains of

the peripheral blood and bone marrow” to “No evidence of leukemic cells in the peripheral blood and/or by routine H/E staining of bone marrow.” [REDACTED]

[REDACTED] In addition, the replacement of “and” with “and/or” was done to align with both ESMO and NCCN guideline regarding the definition of CR. See reference: Grever MR. How I treat hairy cell leukemia. *Blood*. 2010;115(1):21-28.

4. Section 12.5 (Clinical Monitoring) – A new subsection 12.5.1 (Protocol Deviation) was added. [REDACTED]

5. Section 13.3 (Primary Endpoint) – [REDACTED]

6. Section 13.3 (Primary Endpoint) – A sentence was added after the sentence “...review of scanning parameters and associated activities required for study image collection.” The new text is “**Bone marrow slides will be used for response assessment.**” [REDACTED]

7. Section 13.3 (Primary Endpoint) – The text “from bone marrow biopsies/aspirates, reports of CBC” was added to the sentence “Images, pathology slides from bone marrow...” The revised sentence is “Images, pathology slides **from bone marrow biopsies/aspirates, reports of CBC**, and associated documentation must be acquired as instructed in this manual and submitted to the central vendor.” [REDACTED]

8. Section 13.4.1.1 (CR Rate, Duration of CR (Disease-Free Survival), and Duration of Hematologic Remission) – The text “as defined in Section 11.1” was added at the end of to the sentence “Duration of CR (also called disease-free survival) will be

measured ...” The revised sentence is “Duration of CR (also called disease-free survival) will be measured from the first documentation of CR (by imaging, bone marrow biopsy and blood counts) to the time of relapse **as defined in Section 11.1.**”

[REDACTED]

9. Section 13.4.1.1 (CR Rate, Duration of CR [Disease-Free Survival], and Duration of Hematologic Remission) – The sentence “Duration of CR and HR will be censored...” was revised to “Duration of CR will be censored on the date of the last disease assessment or clinical response assessment for subjects who have no documented relapse prior to data cutoff, dropout, or the initiation of alternative anticancer therapy.” A new sentence explaining how the duration of HR will be censored was added as follows: “Duration of HR will be censored on the date of the last evaluable hematologic assessment for subjects who have no documented loss of HR prior to data cutoff, dropout, or the initiation of alternative anticancer therapy.”
- [REDACTED]
- [REDACTED]

[figure not shown]
10. Section 13.4.1.4 (Duration of Objective Response) – The text “as defined in Section 11.1” was added at the end of the sentence “Duration of objective response will be measured...” The revised text is “Duration of objective response will be measured from the first documentation of objective response to the event of relapse as defined in Section 11.1.”
- [REDACTED]

11. Section 13.4.1.5 (Progression-Free Survival) – The text “PFS is measured from the start of moxetumomab pasudotox administration to relapse, PD, initiation of alternative anticancer therapy, or death from any cause (Saven et al, 1998; Else et al, 2009)” was changed to “PFS is measured from the start of moxetumomab pasudotox administration to relapse, PD, or death from any cause.”
- [REDACTED]
- [REDACTED]

12. Section 13.4.1.5 (Progression-Free Survival) – The text “PFS will be censored on the last hematologic assessment for subjects without relapse, PD, alternate therapy, or death” was changed to “PFS will be censored on the last hematologic assessment for subjects without relapse, PD, or death.”
- [REDACTED]
- [REDACTED]

